3.1.3.1.3. Duration of Each Local Reaction

The duration of each local reaction will be calculated in days as the resolution date of reaction - start date of reaction + 1. Resolution of the event is the last day on which the event is recorded in the e-diary (or AE CRF) or the date the event ends if it is unresolved during the participant's e-diary recording period (end date collected on the CRF) or AE stop date, whichever is longer, unless chronicity is established.

If there is no known end date, the duration will be considered unknown and set to "missing." Participants with no reported reaction have no duration.

As there is a second vaccination at Visit A102, the date the reaction ended for Vaccination 1 should not be after the beginning of Vaccination 2. Therefore, if a reaction is ongoing at the time of Vaccination 2, the end date for the reaction after Vaccination 1 would be the date of the day before Vaccination 2, which will be used for the duration computation.

For the vaccine group receiving sequential administration of qIRV/RSVpreF, the duration will be calculated as total days after Vaccination 1 and Vaccination 2.

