8.3.4.2. Local Reactions

During the reactogenicity e-diary reporting period, participants will be asked to assess redness, swelling, and pain at the injection site and to record the symptoms in the reactogenicity e-diary.

If a local reaction persists beyond the end of the reactogenicity e-diary period following vaccination, the investigator will enter this information into the CRF and follow up at the next study visit to obtain stop dates for local reactions that have resolved.

Participants will be provided with a measuring device. Redness and swelling will be measured and recorded in measuring device units (range: 1 to 21) and then categorized during analysis as absent, mild, moderate, or severe based on the grading scale in Table 1. Measuring device units can be converted to centimeters according to the following formula: 1 measuring device unit = 0.5 cm. Pain at the injection site will be assessed by the participant as absent, mild, moderate, or severe according to the grading scale in Table 1.

If a Grade 3 local reaction is reported in the reactogenicity e-diary, a telephone contact should occur to ascertain further details and determine whether a site visit is clinically indicated. Only an investigator or medically qualified person can classify a participant's local reaction as Grade 4. If a participant experiences a confirmed Grade 4 local reaction, the investigator must immediately notify the sponsor and, if it is determined to be related to the administration of the study intervention, further vaccinations will be discontinued in that participant.

		•		
	Mild Grade 1	Moderate Grade 2	Severe Grade 3	Grade 4ª
Pain at the injection site	Does not interfere with activity	Interferes with activity	Prevents daily activity	Emergency room visit or hospitalization for severe pain
Redness	>2.0 cm to 5.0 cm (5 to 10 measuring device units)	>5.0 cm to 10.0 cm (11 to 20 measuring device units)	>10 cm (≥21 measuring device units)	Necrosis or exfoliative dermatitis
Swelling	>2.0 cm to 5.0 cm (5 to 10 measuring	>5.0 cm to 10.0 cm (11 to 20 measuring	>10 cm (≥21 measuring	Necrosis

Table 1. Local Reaction Grading Scale

device units)

device units)

device units)

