3.1.3.2. Systemic Events

Systemic events, including fever, fatigue, headache, vomiting, nausea, diarrhea, chills, new or worsened muscle pain, and new or worsened joint pain, are reported from Day 1 through Day 7 after vaccination, where Day 1 is the day of vaccination with combination RSVpreF + qIRV, qIRV, RSVpreF, or placebo. The derivations for the systemic events, for each of the 5 vaccine groups as described below, will be handled similarly to the way local reactions are handled for the presence for each participant, severity level, duration, onset day, and systemic event on each and any day:

- 1. Presence (yes or no) of each systemic event on any day (Day 1 through Day 7) after vaccination.
- 2. Presence (yes or no) of any systemic event on any day (Day 1 through Day 7) after vaccination.
- 3. Maximum severity of each systemic event on any day (Day 1 through Day 7) after vaccination.
- 4. Maximum severity of any systemic event on any day (Day 1 through Day 7) after vaccination.
- 5. Duration of each systemic event after vaccination.
- 6. Onset day of each systemic event after vaccination.
- 7. Presence (yes or no) of each systemic event on each and any of the 7 days after Vaccination.
- 8. Presence (yes or no) of any systemic event on each and any of the 7 days after Vaccination.

The grading scale for systemic events is provided in the protocol. However, the derivation of severity of each systemic event on each day should be based on the maximum severity reported from the e-diary or the AE CRF, if data are reported from both sources; or the e-diary alone if not reported from the AE CRF.

Fever is defined as a temperature of $\geq 100.4^{\circ}$ F ($\geq 38.0^{\circ}$ C). The highest temperature for each day will be recorded in the e-diary. For reporting purposes, fever will be analyzed using the following temperature ranges:

- Mild (\geq 38.0 to 38.4°C from the e-diary or mild grade from the AE CRF).
- Moderate (>38.4 to 38.9°C from the e-diary or moderate grade from the AE CRF).
- Severe (>38.9 to 40.0°C from the e-diary or severe grade from the AE CRF).
- Grade 4 (>40.0°C from the e-diary or severe grade from the AE CRF plus documented >40.0°C in CRF query or other sources).

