6.1.3.2. Supplementary Analysis

To support the assessment of reactogenicity, the following endpoints, as specified in Section 3.1.3.1, will be summarized per the supplemental analysis with the same analysis population:

- Duration (days) of each local reaction and each systemic event after vaccination.
- Onset day of each local reaction and each systemic event after vaccination.
- Presence of any local reaction and any systemic event on each of the 7 days, for the first 2 days (with nonmissing reactogenicity data from Day 1 through Day 2), first 3 days, first 4 days, first 5 days, first 6 days, all 7 days (nonmissing reactogenicity data for all 7 days), and for "any day (Day 1 through Day 7)."

The presentation of the results will include a basic descriptive summary without the 95% CIs (Section 5.2.1).

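### Duration of reactions: a reaction still ongoing at the last contact is set to missing, while one ongoing at Vaccination 2 is kept at about 22 to 35 days

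*SAP*

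**What the plan says.** SAP 3.1.3.1.3 defines the duration of each local reaction as "calculated in days as the resolution date of reaction - start date of reaction + 1". It then treats a reaction that has not ended in two ways.

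- No end date known: "If there is no known end date, the duration will be considered unknown and set to" missing.
- Ongoing at Vaccination 2 (Substudy A only): "the end date for the reaction after Vaccination 1 would be the date of the day before Vaccination 2", and that date enters the computation.

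The section has no rule for a reaction still ongoing at A103, B102 or an early-withdrawal contact. Its definition of resolution carries the qualifier "whichever is longer, unless chronicity is established", but the SAP does not say what chronicity is or what duration then applies.

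On data collection, Protocol 8.3.4.2 has the investigator "follow up at the next study visit to obtain stop dates for local reactions that have resolved". Protocol 8.3.4.3 says the same for systemic events. SAP 5.3.1.1 adds no imputation beyond SAP 3.1.3 and plans no sensitivity analysis.

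The rule reaches beyond local reactions. Under SAP 3.1.3.2, systemic events "will be handled similarly to the way local reactions are handled for the presence for each participant, severity level, duration" and so on. SAP 3.4.1 derives antipyretic use similarly, and SAP 6.2.3.1 summarises its duration. SAP 3.2.1 and 6.1.6 carry the definitions and presentation into Substudy B. The planned output in SAP 6.1.3.2 is "Duration (days) of each local reaction and each systemic event after vaccination", as a descriptive summary without confidence intervals.

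**The concern.** Whether a duration is missing depends on the duration itself. A reaction that ends before the last visit can be given a date and counted. One that outlasts the last visit, with no later stop date, is not counted. The summary then describes reactions with a known end rather than all reactions, and the longest are the ones removed.

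The treatment also differs by vaccination within Substudy A. After Vaccination 1 (the combination and qIRV-alone columns) a persistent reaction is kept, cut off at Vaccination 2, provided that Vaccination 2 is given. After Vaccination 2 (the RSVpreF-alone and placebo columns) it is lost. Combination versus qIRV is treated alike; combination versus RSVpreF alone is not. For the sequential qIRV/RSVpreF column, duration is the total over both vaccinations, and the SAP does not say what the total is if one part is missing.

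Substudy B compares two formulations that may differ in injection-site reactogenicity, with a view to selecting one. A local reaction lasting four weeks would be relevant to that comparison, yet it would not appear in the mean or maximum duration of either arm.

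**Working it through.** The documents give no figure for duration, so there is nothing of the plan's to reproduce. The check has two parts.

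**1. What each rule gives for a persistent reaction**

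Inputs: Day 1 is the day of vaccination and the e-diary covers Days 1 to 7 (SAP 3.1.3.1). Vaccination 2 falls 28 to 35 days after Vaccination 1, A103 falls 28 to 35 days after Vaccination 2, and B102 falls 28 to 35 days after the single vaccination (Protocol Tables 4 and 7). Let w be that interval and d the onset day.

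- Ongoing at Vaccination 2: Vaccination 2 is on Day w + 1, so the end date is Day w and duration = w − d + 1.
- Ongoing at the last visit: the visit is on Day w + 1, so the reaction has lasted at least (w + 1) − d + 1 days, counting the visit day.

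| | Onset Day 1 | Onset Day 7 |
|---|---|---|
| Ongoing at Vaccination 2, w = 28 | 28 | 22 |
| Ongoing at Vaccination 2, w = 35 | 35 | 29 |
| Ongoing at last visit, w = 28 | at least 29, recorded as missing | at least 23, recorded as missing |
| Ongoing at last visit, w = 35 | at least 36, recorded as missing | at least 30, recorded as missing |

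Reactions of similar length are thus recorded as 22 to 35 days in one case and as missing in the other.

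**2. Illustration of the effect on the mean**

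Protocol 10.10.11.5 assumes that 65% of 1.0-mL recipients report at least one local reaction. With 100 per group that is 65 reactors; in one age group of 50 it is 32.5, taken as 33. Assumptions not in the documents: the other reactions average 2 days, and k reactions are ongoing at the earliest B102 (w = 28), each having lasted L = 23 (onset Day 7) to 29 (onset Day 1) days.

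Mean ≥ [(n − k) × 2 + k × L] / n

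- n = 65, k = 1: (128 + 23)/65 = 2.32 to (128 + 29)/65 = 2.42
- n = 65, k = 2: (126 + 46)/65 = 2.65 to (126 + 58)/65 = 2.83
- n = 33, k = 1: (64 + 23)/33 = 2.64 to (64 + 29)/33 = 2.82

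Under the SAP rule the reported mean is 2.00 in every case. The true maximum is at least 23 to 29 days, but the reported maximum comes from the remaining reactions only. The median moves by half a rank for each reaction lost. Because 65% refers to any local reaction, the number of reactors for one specific local reaction is no larger, and one lost case weighs at least as much. The figure does not apply to systemic events.

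**The case against.** The strongest reply is that a stop date will usually exist. Protocol 8.3.4 obliges the investigator to obtain stop dates for anything ongoing on the last completed e-diary day, with no stated limit to the next visit. SAP 3.1.3.1.3 also accepts an AE stop date, and Protocol 8.4.1 lets AE follow-up run past the last visit. This stands in part: loss is not certain in every case. But Protocol 8.3.4 says that e-diary data are not reported as AEs, the schedules place no stop-date step after A103, B102 or the early-withdrawal contact, and none of these provisions gives a value to a reaction unresolved at last contact. The chronicity qualifier shows that persistent reactions were thought of, but it is undefined. If the last e-diary day were instead taken as resolution, a reaction of 23 days or more would be recorded as ending by Day 7.

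It is also fair that the effect is small. Duration is supplementary, the primary summaries of presence and maximum severity are untouched, and a duration n below the number of reactors would show that something is missing, though not why. The documents give no frequency for reactions this long.

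Some stronger readings are tempting but unsupported:

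- **A breach of the treatment-policy estimand.** That estimand (SAP 2.2.1.3.1 and 2.2.2.1.1) concerns rates of e-diary items on Days 1 to 7 after intercurrent events. Duration is not its variable, and a missing stop date is not an intercurrent event.
- **Columns that are not comparable in general, or a bias that always runs one way.** Combination and qIRV share a rule, as do both Substudy B arms. Losing an ongoing reaction shortens a group's reported mean, but a resolved reaction with a lost date could be of any length. Any bias between the Substudy B arms depends on which has more persistent reactions, which is unknown.
- **A distorted formulation choice.** No passage names duration as a selection criterion.

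**Conclusion.** The point holds as a minor gap in the SAP. A reaction ongoing at last contact, with no later stop date, is dropped from the duration summary because it is long, whereas the same section keeps a comparable reaction ongoing at Vaccination 2. The mean and maximum can be understated in the RSVpreF-alone and placebo columns of Substudy A and in both arms of Substudy B; the same applies to systemic events and antipyretic use.

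Under the stated assumptions, one or two such reactions among 65 reactors put the mean at least 0.3 to 0.8 days above the reported 2.0. If every reaction has a known end date, there is no effect. The exclusion is inferred from the set-to-missing rule together with the absence of imputation; the SAP does not state it in those words. The change is a cheap improvement and not a condition for the primary analysis.

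**What to change.** In SAP 3.1.3.1.3, and through it 3.1.3.2, 3.2.1 and 3.4.1, add a rule for a reaction ongoing at the last contact (A103, B102 or early withdrawal) with no later stop date. Set its end date to the date of that contact, flag the duration as a censored minimum, and report the number of such participants per group beside the duration summary. Keep missing only for a reaction known to have resolved on an unknown date. This extends the SAP's own Vaccination 2 convention.

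The cost is one sentence in the SAP and a small programming change, with no new data. The downside is that a flagged duration is a lower bound, so the mean is still understated, though less than under the current rule. That is why the count per group should accompany it.

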3.1.3.1.4. Onset Day of Each Local Reaction

The onset day of each local reaction will be derived. Onset day is defined as the first day of reporting any severity.

For the onset day of each local reaction, if the participant reports changes in severity of the local reaction, only the first day of reporting that specific local reaction will be counted.

For the vaccine group receiving sequential administration of qIRV/RSVpreF, the onset day will be calculated as the earliest day of onset after Vaccination 1 and after Vaccination 2.

3.1.3.1.5. Presence of Each and Any Local Reactions on Each Day and Any Day

Presence (yes or no) of each and any local reaction on each of the 7 days (Day 1 through Day 7) follows the derivation as described in Table 6.

Table 6.Derived Variables for Each and Any Local Reaction on Each Day and Any
Day

Variable	Yes (1)	No (0)	Missing (.)
Each local reaction on a specific day	The participant reports the reaction on a specific day for a specific local reaction.	The participant reports the reaction as "no" on that specific day.	The participant reports the specific local reaction as missing on that specific day.
Any local reaction on a specific day	The participant reports the reaction on a specific day for any of the 3 local reactions.	The participant reports the reactions as "no" or a combination of "no" and missing on that specific day across all 3 local reactions.	The participant reports all 3 local reactions as missing on that specific day.

DMB02-GSOP-RF02 7.0 Statistical Analysis Plan Template 31-Jan-2022 PFIZER CONFIDENTIAL TMF Doc ID: 98.03 Page 22 of 46

Variable	Yes (1)	No (0)	Missing (.)
Each local	The participant reports that	The participant reports the local reaction as "no" or a combination of "no" and missing across all 7 days.	The participant reports
reaction on any	local reaction on any day		the local reaction as
day	(Days 1-7).		missing on all 7 days.
Any local	The participant reports any local reaction on any day (Days 1-7).	The participant reports the reactions	The participant reports
reaction on any		as "no" or missing across all 7 days	all 3 local reactions as
day		and across all 3 local reactions.	missing on all 7 days.

Table 6.	Derived Variables for Each and Any Local Reaction on Each Day and Any
	Day

For the vaccine group receiving sequential administration of qIRV/RSVpreF, if a local reaction is present on Day x either after Vaccination 1 or after Vaccination 2 for the same participant, that local reaction is considered as present on that day.

3.1.3.2. Systemic Events

Systemic events, including fever, fatigue, headache, vomiting, nausea, diarrhea, chills, new or worsened muscle pain, and new or worsened joint pain, are reported from Day 1 through Day 7 after vaccination, where Day 1 is the day of vaccination with combination RSVpreF + qIRV, qIRV, RSVpreF, or placebo. The derivations for the systemic events, for each of the 5 vaccine groups as described below, will be handled similarly to the way local reactions are handled for the presence for each participant, severity level, duration, onset day, and systemic event on each and any day:

- 1. Presence (yes or no) of each systemic event on any day (Day 1 through Day 7) after vaccination.
- 2. Presence (yes or no) of any systemic event on any day (Day 1 through Day 7) after vaccination.
- 3. Maximum severity of each systemic event on any day (Day 1 through Day 7) after vaccination.
- 4. Maximum severity of any systemic event on any day (Day 1 through Day 7) after vaccination.
- 5. Duration of each systemic event after vaccination.
- 6. Onset day of each systemic event after vaccination.
- 7. Presence (yes or no) of each systemic event on each and any of the 7 days after Vaccination.
- 8. Presence (yes or no) of any systemic event on each and any of the 7 days after Vaccination.

The grading scale for systemic events is provided in the protocol. However, the derivation of severity of each systemic event on each day should be based on the maximum severity reported from the e-diary or the AE CRF, if data are reported from both sources; or the e-diary alone if not reported from the AE CRF.

Fever is defined as a temperature of $\geq 100.4^{\circ}$ F ($\geq 38.0^{\circ}$ C). The highest temperature for each day will be recorded in the e-diary. For reporting purposes, fever will be analyzed using the following temperature ranges:

- Mild (\geq 38.0 to 38.4°C from the e-diary or mild grade from the AE CRF).
- Moderate (>38.4 to 38.9°C from the e-diary or moderate grade from the AE CRF).
- Severe (>38.9 to 40.0°C from the e-diary or severe grade from the AE CRF).
- Grade 4 (>40.0°C from the e-diary or severe grade from the AE CRF plus documented >40.0°C in CRF query or other sources).

If a participant reports a fever (or severity of fever) by mistake, the correct temperature will be transcribed in a data-handling memo to be included in the analysis, and the temperature that is confirmed as incorrect will not be included in the analysis.

3.1.3.3. Adverse Events

Standard algorithms for handling missing AE dates and missing AE severity will be applied as described in the Pfizer vaccine data standard rules.

For any AE reported in the CRF that was considered as reactogenicity (Section 3.1.3) during the clinical review and data-pooling process, this AE record will not be included in any of the derivations included in Section 3.1.3.3 and Section 3.1.3.4. However, if those reactogenicity AEs lead to discontinuation or were serious AEs, they will still be included in AE data.

The following derivations will be included for each participant:

- 1. Any AE reported within 1 month after vaccination: If the AE started on the same day of vaccination, and the AE start time is before the vaccination time, then this AE will not be counted. Otherwise, if the AE start time is missing or after the vaccination time, the AE will be included.
- 2. Any related AE reported within 1 month after vaccination: This is similar to the above except only the related AE is included (but excluding the related reactogenicity reported within 7 days of vaccination [Section 3.1.3]).
- 3. Any immediate AE reported after vaccination (AE start time is within 30 minutes after vaccination): Only those AEs that start on the same day of vaccination, and with nonmissing AE start time that is within 30 minutes of vaccination, will be included.
- 4. Any severe AE reported within 1 month after vaccination.

- 5. Any life-threatening AE reported within 1 month after vaccination.
- 6. Any AE leading to study withdrawal within 1 month after vaccination.
- 7. Any SAE reported within 1 month after vaccination.
- 8. Any AESI within 1 month after vaccination, based on the AE PT.

The following events are considered AESIs:

- Confirmed diagnosis of influenza.
- Confirmed diagnosis of RSV infection.
- Confirmed diagnosis of myocarditis or pericarditis within 4 weeks after Vaccination 1. See Section 3.6.3 for the evaluation of potential myocarditis or pericarditis.

Each of the above will be derived for the data presentation with 5 vaccine groups. Specifically, for the vaccine group receiving sequential administration of qIRV/RSVpreF, the endpoints will be derived after Vaccination 1 and Vaccination 2.

